The Effect of Intravenous EACA on Blood Loss and Transfusion Requirements After Bilateral VRO

Protocol and Analysis Plan

NCT # NCT02257580

Approved 12/10/2014

1. What is the Study Design

Experimental:

Randomized controlled clinical trial (RCT)

2. Who will be recruited and enrolled?

Inclusion Criteria:

Patients will be recruited from the practices of [name] and [name]. Inclusion criteria will include the following:

- Age less than or equal to 18
- Scheduled for elective bilateral VRO with or without associated soft tissue and osseous procedures

Exclusion Criteria:

All patients will be asked to discontinue acetylsalicylic acid (ASA), antiplatelet agents, and hormone replacement and hormonal contraceptive agents at least 7 days prior to surgery. Other than ASA, these agents will be held 6 weeks postoperatively.

- Preoperative use of an anticoagulant (Plavix, warfarin, lovenox, etc.)
- History of hypersensitivity to EACA
- History of thromboembolic event (e.g., PE or DVT)
- History of renal insufficiency or failure
- Congenital or acquired coagulopathy as evidence by INR >1.4 or PTT > 1.4 times normal, or Platelets <150,000/mm³ on preoperative laboratory testing
- Use of hormone replacement therapy or hormonal contraceptive agent within 7 days prior to surgery
- Pregnant
- Breastfeeding
- Older than 18 years of age
- Patients not receiving neuraxial anesthesia

This trial will be registered on ClinicalTrials.gov. All patients undergoing bilateral VRO by the study surgeons ([name]) will be identified in their office and screened for eligibility as potential patients for participation in the study. A research assistant will review the office and operative calendars of the study surgeons each week to identify and recruit potential patients. The assistant will record on the CONSORT diagram any reasons for ineligibility/exclusion.

The surgeon, a co-investigator or research assistant will obtain consent prior to surgery, at the patient's preadmission screening visit. All authors on the protocol, in addition to their research assistants, will be designated to obtain consent.

We will power the study to detect a 250mL difference in calculated intra-operative blood loss between groups. This effect size has been used in the total hip literature, and it is considered to be a clinically significant difference in blood loss¹⁵. Our analysis shows that 12 patients are required in each arm of the study (24 patients total) to achieve 81% power with an independent-sample t-test and statistical significance set to alpha equal to 0.05. Expecting that 10-25% of patients will be excluded, we will aim to enroll a total of 30 patients in this study.

Patients aged 18 or younger will be screened for study eligibility

3. Interventions or Observations – what data are going to be collected and from what source?

Only anesthesiologists agreeing to participate in the study will be paired with the study surgeons. Anesthesia will be conducted in a standardized fashion. The anesthesiologist will perform a neuraxial block (epidural, spinal, combined-spinal epidural) as well as administer general anesthesia. A neuraxial block will be placed using bupivicaine. A balanced general anesthetic utilizing a combination of either isoflurane, sevoflurane with or without nitrous oxide, vecuronium, midazalam and either fentanyl, morphine or dilaudid as the narcotic will be used at the discretion of the anesthesiologist. If a combined-spinal epidural is unsuccessful and an epidural and/or spinal are successfully obtained, the patient will still be included in the study. Patients not receiving neuraxial anesthesia will be excluded from the study. Arterial and venous access will be obtained in the usual sterile manner for monitoring.

The blood pressure target will be 20-25% below baseline, which will be achieved primarily with the combination of the general anesthesia and the neuraxial anesthesia. For blood pressure above this range, the epidural will be dosed with a short-acting local anesthetic, and/or the depth of the general anesthetic and will be titrated as per the anesthesiologist's judgment. For hypotension below this range, intravenous pressors, crystalloid, colloid or blood will be given. The technique of induced hypotension will not be utilized during these cases. Additional maintenance IV fluids or colloid will be given to maintain urine output of at least 0.5-1ml/kg/hr. Toradol and IV acetaminophen may be given towards the end of the case per the anesthesiologist's discretion.

Bilateral VRO will be performed as per the surgeon's routine practice. In general, the operative extremity will be prepped and draped in the usual sterile fashion. Prior to incision, the anesthesiologist will administer a loading dose of 100 mg/kg of EACA with a max of 4-5 grams up to 1 hour prior to incision. During the case, an infusion of 33 mg/kg/hr (max of 1 gram/hr) will be maintained. The use of EACA will be terminated at the end of the case. Patients randomized to the placebo arm will be

infused with a comparable volume of normal saline prepared by the pharmacy. All participating anesthesiologists will not be blinded in this study. A direct lateral approach to the femur will be used, and standard surgical techniques for intra-operative hemostasis will be utilized. The surgeon will perform bilateral femoral osteotomies and associated soft tissue surgery and pelvic osteotomy. After all hardware is placed, the wound will be thoroughly irrigated and suctioned. A deep drain will be placed on each operative side, and the wound will be closed in layers. Intra-operatively, a cell saver will be used, and the volume (mL) of auto-transfusion will be recorded.

Hematocrit levels will be monitored regularly in the post-operative period. As per protocol, a post-op hematocrit will be drawn in the PACU, and subsequently, daily labs will be obtained unless specified by the medicine or surgical attending. Routine, daily inpatient CBC data and drain output will be reviewed. Inpatient and office records will be accessed to help identify postoperative complications. The criteria for transfusion of blood products will be a hemoglobin level of < 7.0 g/dL or a hemoglobin level of < 10.0 g/dL with clinical signs of symptomatic anemia (e.g., unexplained tachycardia, hypotension unresponsive to fluids or vasopressors, change in mental status, low urine output, and shortness of breath). Blood will be administered 1 unit at a time, and the presence of symptoms or signs will be reassessed after each unit. This algorithm may be altered by the treating physician (e.g., PACU attending, surgeon, pediatrician, or the OR anesthesiologist), however all decisions will be supported by reasonable documentation. Drains will be removed on POD 2 unless specified by the attending surgeon, and the 24-hour clock will begin once the patient is in the PACU. All drains, patient charts, and patient rooms will be clearly labeled in order to identify study patients.

Attending surgeons, orthopedic surgery residents, physician assistants and research assistants involved with this study will assist in data collection. For each patient, we will collect demographic data, pre-operative CBC data, intra-operative cell saver auto-transfusion volumes, post-operative number of packed red blood cell units transfused, post-operative CBC data, post-operative drain outputs, and post-operative complications. This information will be gathered from the peri-operative medical records and electronic medical records.

A sticker will be place on the front of each participating patient's chart identifying him or her as a study patient. Their enrollment will also be communicated in the clinician rounding notes for each patient. Drains will be labeled for each study participant as well, and nurses will record the drain outputs per their floor protocol.

Data recorded from the electronic medical record will include:

- Date of surgery
- Patient age at the time of surgery
- Patient sex
- Patient height (cm) and weight (kg) at time of admission
- Preoperative CBC data and coagulation study data

- Postoperative hemoglobin on all inpatient days postoperatively (g/dL)
- Transfusion requirement during inpatient stay (units required)
- Transfusion reaction
- Total 24-hour drain output
- Postoperative day and time of discharge
- Chart review of progress notes for evidence of clinically significant VTE
- Chart review of progress notes for evidence of reoperation, hematoma, seroma, or postoperative infection

Data recorded from the operating room record will include:

- Anesthetic used (e.g., spinal/epidural, general, etc.)
- Operative times (minutes)
- Intra-operative transfusion requirements (units of blood)
- Use of cell saver intraoperatively (auto-transfusion volume, mL)
- Intra-operative complications

Data recorded from outpatient postoperative office records will include:

- Chart review of progress notes for evidence of clinically significant VTE through six weeks post-operatively
- Chart review of progress notes for evidence of re-operation, hematoma, seroma, or postoperative infection through six weeks post-operatively

Patients will be randomized to either the intervention or control group, as per randomization protocol described elsewhere in the proposal. For patients who are randomized to the control group, study data will be collected in the same manner as for the intervention group.

All tests and imaging used in this study are considered standard of care.

Randomization Process:

The patients will be randomized into one of 2 groups: (1) Loading dose and infusion of EACA (2) Equivalent volume of normal saline prepared by the pharmacy. An EACA loading dose of 100 mg/kg with a max of 4-5 grams will be given up to 1 hour prior to incision. During the case, an EACA infusion of 33 mg/kg/hr (max of 1 gram/hr) will be maintained. The use of EACA will be terminated at the end of the case. Assignment of patients will be made based on a sequential treatment assignment or minimization strategy in order to ensure an even distribution of patients in each treatment arm. More specifically, each patient will be randomized to the treatment arm that would minimize differences between groups. Randomization will be stratified by sex and surgery type (bilateral VRO, bilateral VRO with associated soft tissue or osseous procedure) so that the number of male/female patients and VRO/associated procedure patients will be balanced in each study group between trial arms.

The Biostatistics Core of the HSS Healthcare Research Institute will randomize each patient based on the minimization strategy. It will be a double-blind experiment with all parties, except the pharmacy, anesthesiologist, and designated research assistant, being blinded to the randomization schedule (surgeon, medical staff, and patient). Patient recruitment will continue until a total of 30 patients are enrolled.

Treatment Groups:

Bilateral VROs will be performed as per the study surgeon's routine practice. In general, the operative extremity will be prepped and draped in the usual sterile fashion. Prior to incision, the anesthesiologist, will administer a loading dose of 100 mg/kg of EACA with (max of 4-5 grams) or an equivalent volume of normal saline prepared by the pharmacy. The loading dose may be give up to 1 hour prior to incision. During the case, an EACA infusion of 33 mg/kg/hr (max of 1 gram/hr) will be maintained. Only anesthesiologists agreeing to participate in the study will be paired with the study surgeons, and all anesthesiologists will be aware of a patient's randomization to the treatment or placebo group.

Outcome Measures

Primary outcome: Calculated total blood loss.

Secondary outcomes of interest: Postoperative transfusion requirements (allogeneic blood transfusion and intraoperative cell saver utilization), post-operative blood loss, length of stay, and post-operative complications.

Calculated total blood loss will be determined from the difference between the preoperative hemoglobin and the postoperative hemoglobin (or the lowest postoperative hemoglobin during the hospital stay prior to transfusion). Based on hemoglobin balance, the estimated blood loss will be calculated according to the formula by Nadler et al.¹⁷:

```
Estimated Blood Volume (EBV) = (k_1 \text{ x Height}^3 \text{ (m)}) + (k_2 \text{ x Weight (kg)}) + k_3
For men, k_1 = 0.3669, k_2 = 0.03219, and k_3 = 0.6041
For women, k_1 = 0.3561, k_2 = 0.03308, and k_3 = 0.1833
```

Multiplying the EBV by the hematocrit (Hct) gives the red blood cell (RBC) volume. As such, a change in the RBC volume can be calculated from a change in the Hct level^{23,24}:

```
Total RBC volume loss = EBV x (Hct Preop – Hct Postop)
```

Transfusions (mean volume per unit at HSS, 250 mL) can be taken into account by calculating the total blood loss¹⁶:

Total blood loss (L) = Total RBC volume loss + (No. of Units Transfused x 0.25) / (Hct Preop – Hct Postop) / 2)

The rate of perioperative blood transfusions, both intraoperative and postoperative, will be documented for analysis.

The criteria for transfusion of blood products will be a hemoglobin level of < 7.0 g/dL or a hemoglobin level of < 10.0 g/dL with clinical signs of symptomatic anemia (e.g., unexplained tachycardia, hypotension unresponsive to fluids or vasopressors, change in mental status, low

urine ouput, and shortness of breath). Blood will be administered 1 unit at a time, and the presence of symptoms or signs will be reassessed after each unit. This algorithm may be altered by the treating physician (e.g., PACU attending, surgeon, or the OR anesthesiologist), however all decisions will be supported by reasonable documentation. Drains will be removed on POD 2 unless specified by the attending surgeon. Of note, the chart of the patient will clearly indicate him/her as a study patient.

VTE prophylaxis is not commonly used for pediatric patients at our institution. However, all patients will also receive a comprehensive approach to postoperative care comprised of mechanical (sequential compressive device) prophylaxis in-house, early mobilization with physical therapy, medical optimization, and regional anesthesia (if appropriate).

4. What is the long-term significance?

There are certain risks associated with blood loss and blood transfusion after elective orthopaedic procedures in young patients. Blood loss and transfusion requirements can be reduced with several blood conservation measures, including the use of pharmacological agents such as EACA. If the use of IV EACA is shown to decrease blood loss and transfusion requirements after bilateral VROs, it will provide an efficacious and inexpensive method to reduce post-operative morbidity and improve patient outcomes after bilateral VROs.

D. SAMPLE SIZE AND DATA ANALYSIS

Sample Size -

- 1. Proposed analysis (e.g., student's t-test, ANOVA, chi-square, regression, etc.): Independent samples t-test will be utilized if the data is normally distributed (or non-parametric Mann-Whitney U test if assumption of normality is not met).
- 2. Alpha level: 0.05
- 3. Beta or power level: 0.81
- 4. Primary outcome variable estimate (mean +/- s.d. for continuous outcome, frequency/percentage for categorical variable):

The primary outcome of interest in total intra-operative blood loss, which will be summarized as mean +/- standard deviation. Based on an analysis of the twenty-four consecutive cases of bilateral VROs, the mean calculated intra-operative blood loss was 671.24mL (SD: 233.69).

- 5. Number of groups being compared (use 1 for paired analysis within the same subjects): Two groups are being compared: Treatment Group (Loading Dose + Infusion) vs. Placebo Group (NS)
 - 6. Effect size or change expected between groups: 250cc

- 7. Resulting number per group: 12
- 8. Total sample size required: 24

Data Analysis

The primary outcome of interest (calculated total blood loss) will be presented as a mean +/-standard deviation and compared between the EACA and placebo groups with a two-sample t-test. Multivariable linear regression models will also be used to adjust for any potential confounding due to total blood loss volume between arms after adjustment for age, sex, BMI, and anesthesia type. To adjust for any patients lost due to early withdrawal, we will increase our sample size by 3 patients in each group for a total sample size of 30 patients.

Calculated total blood loss will be determined from the difference between the preoperative hemoglobin and the postoperative hemoglobin (or the lowest postoperative hemoglobin during the hospital stay prior to transfusion). Based on hemoglobin balance, the estimated blood loss will be calculated according to the formula by Nadler et al.¹⁷:

```
Estimated Blood Volume (EBV) = (k_1 \text{ x Height}^3 \text{ (m)}) + (k_2 \text{ x Weight (kg)}) + k_3
For men, k_1 = 0.3669, k_2 = 0.03219, and k_3 = 0.6041
For women, k_1 = 0.3561, k_2 = 0.03308, and k_3 = 0.1833
```

Multiplying the EBV by the hematocrit (Hct) gives the red blood cell (RBC) volume. As such, a change in the RBC volume can be calculated from a change in the Hct level^{23,24}:

```
Total RBC volume loss = EBV \times (Hct Preop - Hct Postop)
```

Transfusions (mean volume per unit at HSS, 250 mL) can be taken into account by calculating the total blood loss¹⁶:

Total blood loss (L) = Total RBC volume loss + (No. of Units Transfused x 0.25) / (Hct Preop – Hct Postop) / 2)

All continuous secondary outcomes such as postoperative allogeneic blood transfusion requirement, intraoperative cell saver utilization, and length of hospital stay, will be analyzed in the same manner as the primary outcome.

Complications will be reported as incidence rates with 95% confidence intervals.

All hypotheses will be evaluated with two-sided tests with statistical significance set at $\alpha = 0.05$.

Bibliography

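### Under the plan's own two-sided test, 12 per arm gives 71% power, not 81%, and about 67% to 76% after the expected exclusions; the powered outcome is also labelled inconsistently

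*Combined protocol and SAP*

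**What the plan says.** **Sample size.** Section 2 (Who will be recruited and enrolled?) states that "12 patients are required in each arm of the study (24 patients total) to achieve 81% power with an independent-sample t-test", with alpha 0.05. Section D repeats this: item 3 reads "Beta or power level: 0.81", item 6 gives a 250 cc difference, and items 7 and 8 give 12 per group and 24 in total. For the variance, item 4 reports from 24 consecutive past cases that "the mean calculated intra-operative blood loss was 671.24mL (SD: 233.69"). Neither place says whether the calculation was one- or two-sided.

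**Test.** The Data Analysis text in section D does say: "All hypotheses will be evaluated with two-sided tests with statistical significance set at" 0.05. It names a two-sample t-test for the primary comparison.

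**Allowance for losses.** Section 2: "Expecting that 10-25% of patients will be excluded, we will aim to enroll a total of 30 patients in this study". Data Analysis, referring to early withdrawals: "we will increase our sample size by 3 patients in each group for a total sample size of 30 patients".

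**Outcome.** Section 2: "We will power the study to detect a 250mL difference in calculated intra-operative blood loss between groups". Section D, item 4: "The primary outcome of interest in total intra-operative blood loss". The Outcome Measures part of section 3 and the Data Analysis text instead give the primary outcome as calculated total blood loss.

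**The concern.** The difference, SD, alpha, group size and type of test are all stated, so the power can be checked directly. A standardised difference of about 1.07 with 12 per arm looks too small for 81% power in a two-sided t-test. If the stated figure belongs to a one-sided test, the trial was sized for a test that its own analysis text rules out.

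This is the only justification given for the sample size. A null result would be read against 81% power that the design does not have, and the type II error would be about half as large again as claimed (29% against 19%).

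The outcome label adds a second uncertainty. The 250 mL difference and the SD are both attached to intra-operative loss. The outcome to be tested is derived from a postoperative hemoglobin, or the lowest in-hospital value before transfusion, so it can include postoperative loss. Postoperative blood loss is also listed as a separate secondary outcome. A reader cannot tell whether the SD belongs to the outcome that will be analysed.

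**Working it through.** **Inputs.** Difference 250 mL (section 2; section D, item 6). SD 233.69 mL (section D, item 4). Alpha 0.05 and 12 per arm (section 2; section D, items 2 and 7). Two-sided testing (section D, Data Analysis). Enrolment 30 with 10% to 25% excluded (section 2).

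**Formula.** For a two-sample t-test with n1 and n2 patients, the noncentrality is λ = Δ / [SD × √(1/n1 + 1/n2)] on n1 + n2 − 2 degrees of freedom (df). Power is the probability that a noncentral t variable exceeds the critical value; for a two-sided test the negligible opposite tail is added.

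**Common quantities at 12 + 12.**
- Standardised difference: 250 / 233.69 = 1.070.
- Standard error: 233.69 × √(1/12 + 1/12) = 95.40 mL.
- λ = 250 / 95.40 = 2.620, df = 22.

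**Reproducing the plan's 81%.** One-sided 0.05, critical value 1.717: power 81.4%. The smallest one-sided n for 81% is 12 per arm, matching the plan on both counts. This is an inference about origin, since the documents do not mention a one-sided test.

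**The plan's own test.** Two-sided 0.05, critical value 2.074: power 70.7%. The choice of method does not close the gap, because the two-sided normal approximation gives Φ(2.620 − 1.960) = 74.6%. To reach 81% two-sided at 12 per arm, the SD would have to be about 206 mL, or the difference about 283 mL. The difference detectable with 80% power is about 280 mL.

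**After exclusions from 30 enrolled.** 30 × 0.90 = 27; 30 × 0.75 = 22.5. Two-sided t-test, near-equal arms:

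| Evaluable | Arms | λ | Power |
|---|---|---|---|
| 22 | 11 + 11 | 2.509 | 66.5% |
| 23 | 11 + 12 | 2.563 | 68.6% |
| 24 | 12 + 12 | 2.620 | 70.7% |
| 27 | 13 + 14 | 2.778 | 76.1% |
| 28 | 14 + 14 | 2.830 | 77.8% |
| 30 | 15 + 15 | 2.930 | 80.7% |
| 32 | 16 + 16 | 3.026 | 83.3% |

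Power is below 80% throughout the expected range. Evaluable numbers fall below the stated 24 only if exclusions exceed 20%, since 24 / 30 = 0.80.

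**Mann-Whitney alternative (section D, item 1).** In a simulation of 5,000 trials with normal data, power at 12 per arm was about 67%, so this fallback does not recover the shortfall.

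**Outcome label.** Two places (section 2; section D, item 4) say intra-operative; two others (Outcome Measures; Data Analysis) say total. Only one calculation is defined anywhere, the hemoglobin/hematocrit formula. The SD may therefore be total loss under another name, or it may be a different quantity. The documents do not settle which.

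**The case against.** The arithmetic is not in dispute. The strongest objections concern how much it matters.

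- *The stated figure is correct for a one-sided test, and the sample-size text gives no sidedness.* True, so the fault may be a mismatch between two parts of the plan rather than a slip in calculation. The analysis text governs the test, however, so the 81% does not describe the planned trial.
- *The SD is itself imprecise.* It comes from 24 cases. Assuming normal data, its 95% confidence interval is about 182 to 328 mL, over which two-sided power at 12 per arm runs from about 90% down to 43%. The gap of ten points lies inside that range. This is a fair caution against reading 70.7% too finely, but it does not support 81%, and it cuts both ways.
- *Regression adjustment may recover power.* The plan also adjusts for age, sex, BMI and anesthesia type. The documents give no R². If it were 0.10 to 0.30 with four covariate degrees of freedom, power at 12 per arm would be about 74% to 84%. But the stated power is for the unadjusted t-test, which is the comparison named first.
- *The low end is slightly pessimistic.* 22.5 was rounded down; 23 evaluable gives 68.6%. Either way it is below 70%.
- *Thirty evaluable gives 80.7%, not quite 81%.* This stands. Holding strictly at or above 81% with equal arms needs 16 per arm.
- *The outcome label is a separate and softer point.* Also fair: its effect on power is unknown.

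**Conclusion.** The concern holds. On the plan's own inputs and two-sided 0.05 test, power for 250 mL is 70.7% at 12 per arm, ten percentage points below the stated 81%. It is about 67% to 76% over the protocol's expected exclusions and reaches 80.7% only if all 30 are analysed. These figures assume an SD of 233.69 mL, normally distributed data, near-equal arms, and exclusions taken from the 30 enrolled.

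Confidence is high for the arithmetic and for the existence of the label contradiction. That a one-sided calculation produced the 81% is only an inference. Whether the SD applies to calculated total blood loss cannot be determined from the documents.

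**What to change.** **Power statement.** Replace it in section 2 and section D with, for example: *With two-sided alpha 0.05 and an SD of 233.69 mL, 12 per arm gives 71% power to detect 250 mL; 22 to 27 evaluable patients give about 67% to 76%; 80.7% is reached only if all 30 (15 per arm) are analysed.*

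**Then choose one:**
- Keep 30 enrolled and disclose power below 80% after the expected exclusions. This needs no extra patients.
- Enrol enough to keep 30 evaluable: 30 / 0.90 = 33.3, so 34, up to 30 / 0.75 = 40. This costs 4 to 10 more patients for 80.7% power. If 81% must be met strictly with equal arms, 32 evaluable means 32 / 0.90 = 35.6, so 36, up to 32 / 0.75 = 42.7, so 43, which is 6 to 13 more.

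**Outcome.** Name calculated total blood loss as the single primary outcome in section 2, Outcome Measures, section D item 4 and Data Analysis, and state what the SD of 233.69 mL measures. If it is a different quantity, recompute the SD and the power from the 24 past cases, provided their hemoglobin/hematocrit and transfusion data exist; the documents do not say whether they do.

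The restatement and relabelling cost only wording and a less favourable power figure.

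### Inclusion depends on a neuraxial block being obtained by an unblinded anesthesiologist, but the plan fixes neither the order of allocation and block nor the analysis population.

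*Combined protocol and SAP*

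**What the plan says.** The exclusion appears in the list in section 2 (Who will be recruited and enrolled) and again in section 3 (Interventions or Observations): "Patients not receiving neuraxial anesthesia will be excluded from the study". The sentence before it in section 3 shows that success of the block matters, not only the anesthetic plan: "If a combined-spinal epidural is unsuccessful and an epidural and/or spinal are successfully obtained, the patient will still be included in the study".

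On timing, section 2 says: "The surgeon, a co-investigator or research assistant will obtain consent prior to surgery", at the preadmission screening visit. Randomization Process says: "The Biostatistics Core of the HSS Healthcare Research Institute will randomize each patient based on the minimization strategy", with no time point. The control product is described there as: "Equivalent volume of normal saline prepared by the pharmacy". The loading dose may be given up to an hour before incision; its order relative to the block is not stated.

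On blinding, section 3 says: "All participating anesthesiologists will not be blinded in this study". Randomization Process agrees, blinding all parties "except the pharmacy, anesthesiologist, and designated research assistant, being blinded to the randomization schedule".

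Data Analysis in section D compares the two groups by t-test, with a supporting regression. It defines no analysis set and does not say how a randomised patient without a block is handled. Section 2 does require reasons for exclusion to be recorded on the CONSORT diagram.

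**The concern.** A randomised comparison is protected only if the groups analysed are the groups randomised, or if any removal is unrelated to arm. Here a patient can be removed because of the outcome of a procedure done by someone who knows the assignment. No misconduct is needed: ordinary discretion over how long to keep attempting a block could differ by arm.

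The block may also be related to the outcome. Section 3 sets a blood-pressure target "which will be achieved primarily with the combination of the general anesthesia and the neuraxial anesthesia", so patients without a block could plausibly bleed differently, although the documents do not quantify any such link. With 12 to 15 patients per arm, losing one to three from one side can move that arm's mean noticeably.

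**Working it through.** **Sequence.** The text leaves two orders open.

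- Allocation before the block: a failed block removes a patient already assigned, and the person placing the block may know the arm. Preadmission consent and pharmacy preparation point this way, but neither fixes the order.
- Allocation and disclosure after the block: a failed block is a pre-allocation exclusion and cannot bias the comparison.

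**The plan's own figures.** None relates to block failure. Section 3 and section D give 12 per arm for 81% power, with a 250 mL difference and SD 233.69 mL (d = 250/233.69 = 1.070). Exact t power at 12 per arm is 0.814 one-sided and 0.707 two-sided, so the stated figure matches a one-sided test although Data Analysis specifies two-sided tests. That is a separate matter. The allowance of 30 leaves 30 × 0.80 = 24 patients at 20% exclusion and 30 × 0.75 = 22.5 at 25%. The 10–25% has no stated cause, and Data Analysis attributes the same six extra patients to early withdrawal.

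**Illustration of possible bias.** Assumptions, not estimates: 15 per arm; k patients lost from one arm only; point-biserial correlation r between being excluded and blood loss of 0, 0.3 or 0.5; SD 233.69 mL. Section D gives that SD for intra-operative loss, whereas the primary outcome is total loss.

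With p = k/15, the excluded and retained means differ by r × SD / √(p(1−p)). Removing the excluded patients shifts the arm mean by p times that difference:

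shift = r × SD × √(p/(1−p))

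| k | √(p/(1−p)) | r = 0 | r = 0.3 | r = 0.5 |
|---|---|---|---|---|
| 1 | √(1/14) = 0.2673 | 0 | 0.080 SD = 18.7 mL | 0.134 SD = 31.2 mL |
| 2 | √(2/13) = 0.3922 | 0 | 0.118 SD = 27.5 mL | 0.196 SD = 45.8 mL |
| 3 | √(3/12) = 0.5000 | 0 | 0.150 SD = 35.1 mL | 0.250 SD = 58.4 mL |

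Against 250 mL, 18.7/250 = 7.5% and 58.4/250 = 23.4%.

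**Sensitivity to the assumptions.**

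- These correlations imply large differences between excluded and retained patients: 0.3 × 233.69/0.4 = 175 mL at the low end (k = 3) and 0.5 × 233.69/0.2494 = 468 mL at the high end (k = 1).
- If the difference is instead assumed to be 100 to 233.69 mL, the shift is k/15 times that: 6.7 to 15.6 mL for k = 1 and 20.0 to 46.7 mL for k = 3.
- The shift is proportional to the SD. If the SD of total loss were 0.75 to 1.5 times the stated value, the largest entry would run from 58.4 × 0.75 = 43.8 mL to 58.4 × 1.5 = 87.6 mL.
- The direction depends on which arm loses patients. Similar losses in both arms would largely cancel.

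**The case against.** The strongest reply is that the harm is conditional at every step. The criterion stands in a pre-surgery eligibility list, so part of it screens out patients never planned for a block. The failed-block group could be close to empty, since no failure rate is given. Bias needs allocation to come first, failures to occur, failures to differ by arm, and failure to be related to blood loss; the documents establish none of these. The exclusion turns on the block rather than on bleeding seen during the operation. If the arm were hidden from the person placing the block, that person's knowledge could not influence the exclusion. All of this stands, and it limits the point to a conditional one.

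It does not remove the point. The text goes beyond screening by tying inclusion to a block being obtained, and it leaves the order and the analysis set open. The regression on age, sex, BMI and anesthesia type cannot restore patients who have been removed.

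A reader might infer more than the documents support:

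- That the whole criterion is known only in the operating room. Only the failed-block part is learned after consent.
- That randomised patients will certainly be removed by arm. The order is not stated.
- That the 10–25% allowance is a forecast of failed blocks. No cause is given for it.
- That the bias favours EACA. Nothing fixes its direction.
- That allocating after the block would make a named population unnecessary. Data Analysis expects early withdrawals, so one is needed in either case.

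**Conclusion.** The point holds in conditional form. The plan contains a rule that, if allocation precedes the block, lets someone who knows the arm cause a randomised patient to be removed; it does not rule out that order or name a primary population. If allocation and disclosure follow the block, the rule is ordinary eligibility and only the unnamed population remains.

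The actual size cannot be computed. The range of about 19 to 58 mL rests wholly on the assumed one-sided losses, the assumed correlations of 0.3 to 0.5 and an SD for intra-operative loss; it is zero if exclusion is unrelated to blood loss. This should be corrected because the remedy is inexpensive. It is not evidence that the trial's comparison is biased.

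**What to change.** 1. Make the primary analysis all randomised patients who have surgery, in their assigned arm, whether or not the block succeeded. Keep the block-successful patients as a sensitivity analysis. Let the same set govern later withdrawals, as far as outcome data exist.
2. State when allocation is made and when it is disclosed to the anesthesiologist, relative to the block. If the Biostatistics Core and the pharmacy can feasibly allocate and disclose only after the block, failed blocks become pre-allocation exclusions. The primary population must still be named.
3. Report every post-allocation exclusion by arm, with its reason, on the CONSORT diagram.

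Cost: items 1 and 3 need little beyond text. Section 3 already collects the anesthetic used and the outcome data, and section 2 already records reasons for exclusion, so only the split by arm is new. The primary analysis would carry slightly more anesthetic heterogeneity. The sponsor must reconcile the exclusion wording in sections 2 and 3, and the blood-pressure text that relies on the block, with keeping such patients in the analysis; no clinical rule is proposed here. Allocating after the block costs more, because minimisation and pharmacy preparation would have to fit between the block and the loading dose, and the documents give no times for either.
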